Specific Aim 2: To explore the adjunctive intervention's acute efficacy in treating emotional distress (anxiety, depression, suicidal ideation, NSSI) and indices of SUD (commitment to sobriety, craving, quantity and frequency of substance use).

Hypothesis 2a. UP participants will evidence greater decreases in Overall Anxiety Severity and Impairment Scale (OASIS) and Overall Depression Severity and Impairment Scale (ODSIS) from pre- to post-treatment than the those in the control condition. Hypothesis 2b. UP participants who report past month suicidal thoughts at baseline will evidence greater reductions in Beck Scale for Suicidal Ideation (BSI⁴⁹) scores from pre-to post-treatment than those in the control condition.

Hypothesis 2c. UP participants who report past month NSSI urges or episodes at baseline will report a lower frequency of NSSI urges and episodes in a one-month period on the Self-Injurious Thoughts and Behaviors Interview-Clinician Rated [SITBI-CR⁵⁰]-

and on the Self-Injurious Thoughts and Behaviors Interview-Self-Rated [SITBI-SR⁵⁰] at post-treatment than the control.

Hypothesis 2d. UP participants will evidence greater increases in Commitment to Sobriety Scale (CSS⁵¹) and decreases in Craving Scale⁵² scores from pre- to post-treatment than the control.

Hypothesis 2e. UP participants will report lower quantity and frequency of substance use during the study period than those in the control condition.

III. SUBJECT SELECTION

We propose to conduct a pilot randomized controlled trial for young adults with SUD and comorbid emotional distress who are entering into or currently engaged in treatment within a comprehensive outpatient program (ARMS at MGH). We plan to enroll 50 young adults (ages 18 to 26) with SUD and comorbid emotional distress from ARMS. They will be randomized in a 2:1 ratio to one of two conditions: 16 twice-weekly sessions of a transdiagnostic, group-based CBT intervention (the Unified Protocol [UP]) plus usual services at ARMS (UP + TAU condition) or treatment as usual at ARMS (TAU; control condition). All potential subjects must satisfy the following inclusion/exclusion criteria upon the study screening visit:

Inclusion criteria:

- 1. Young adults ages 18 to 26, inclusive
- 2. English language proficiency
- 3. Ability to provide written, informed consent
- 4. Ability to attend in-person, outpatient sessions

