TAU condition: After randomization, participants randomized to the TAU condition will undergo usual care at ARMS for the next 8-10 weeks. Usual care at ARMS typically consists of a combination of up to 3 group therapy sessions per week, individual weekly therapy, and/or psychopharmacology appointments as needed. Some ARMS patients are offered and choose to engage in all three treatment modalities (group therapy, individual therapy, and psychopharmacology), whereas others only engage in one treatment modality. No requirements will be placed on TAU participants with regard to TAU dosage and TAU will be consistent with each participant's clinical treatment plan at ARMS; however, TAU attendance (e.g., number of appointments) for all participants will be tracked by study staff. Four to 6 weeks after randomization, TAU participants will complete a mid-treatment assessment, during which they will complete the same self-report questionnaires (plus TLFB and concomitant treatment log with a study clinician) administered at the screening/baseline visit (see *Measures*). Eight to 10 weeks after randomization, they will repeat the same measures for the in-person "post-treatment" assessment. During both the mid- and post-treatment assessments, should a participant report suicidal thoughts in the past week on the SITBI-SR or clinically significant increases in NSSI, a clinical risk assessment (including severity of ideation and presence of plan, intent, and access to means) will be conducted by a study clinician in order to ensure participant safety and that the

participant remains stable to be treated in an outpatient setting. After completing the post-treatment assessment, their study participation will be complete.

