UP + TAU condition: After randomization, participants randomized to the UP + TAU condition will undergo TAU at ARMS and be offered 16 additional, twice-weekly group UP sessions, also at ARMS (see *Intervention*). Participants in the UP + TAU condition will undergo the same midand post-treatment assessments as the TAU condition, plus the CSQ-8 and a semi-structured interview to collect feedback about the intervention (see *Measures*). The mid-treatment assessment will occur after each participant's 8th UP session OR between 4-6 weeks after randomization, and the post-treatment assessment will occur within two weeks after each participant's 16th UP session. The same risk assessment procedures for mid- and post-treatment assessments used in the TAU condition will also apply to the UP + TAU condition. Should a UP + TAU participant condition have two consecutive unplanned absences from a UP group session, up to three attempts to contact will be made regarding their absence. There will not be a maximum number of missed UP sessions warranting a participant to step out of the 16-session group protocol. After completing the post-treatment assessment, their participation in the study will be complete.

Group UP sessions will take place at the ARMS program at MGH. Study assessment visits (screening/baseline, mid-treatment, and post-treatment) may take place at the ARMS program, the Depression Clinical and Research Program (DCRP), or the Center for Addiction Medicine (CAM) at MGH. Study staff may walk participants between ARMS and the DCRP or CAM as needed.

In sum, the proposed study involves the following points of contact: (1) obtaining informed consent and screening/baseline assessment, (2) mid-treatment assessment involving self-report questionnaires and TLFB, (3) post-treatment assessment involving self-report questionnaires and TLFB (primary endpoint), and (4) 16 twice-weekly group UP sessions for those randomized to the UP + TAU condition.

If participants are unable to complete the clinician-rated measures in-person at their mid- or post-treatment assessments, they will be given the option to complete this portion of the visit via phone call with a study clinician. Should any risk issues arise, the clinician will complete a risk assessment while on the phone with the participant. A licensed clinician will always be on-site for consultation as needed during assessments conducted over the phone.

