If participants are unable to complete the self-reported measures in-person at their screening/baseline, mid-treatment, or post-treatment assessments, they will be e-mailed a link to the self-report battery in Redcap to complete remotely. Study staff will review the completed SRQ assessment in Redcap within 24 (business) hours of submission for report of suicidal thoughts, and within one week to assure their completeness. Should a participant report suicidal thoughts in the past week on the SITBI-SR, a clinical risk assessment (including severity of ideation and presence of plan, intent, and access to means) will be conducted over the phone by a study clinician to ensure participant safety and that the participant remains stable to be treated in an outpatient setting. Additionally, a clinical risk assessment will be conducted over the phone by a study clinician in response to reports of increased NSSI that are deemed clinically

significant. Up to three attempts to contact will be made for this risk assessment before calling a participant's designated emergency contact.

Participants may receive recruitment and scheduling messages, as well as appointment reminders via e-mail or text message over the course of the study, depending on their preferred method of communication. Up to three consecutive (unanswered) contact attempts to the participant will be made for participants in both conditions to schedule mid- and post-treatment assessments. If a participant misses the mid-treatment assessment, but is still responsive to contact attempts, they will still be able to complete the post-treatment assessment. If a participant in either condition is unresponsive to three consecutive unanswered contact attempts within a three-week period at any point within the 10-week study, they will be considered dropped out from the study and no further follow-up will be made; the ARMS clinical team will also be notified.

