Emotion Regulation Questionnaire (ERQ⁵⁵). The ERQ is a 10-item self-report measure assessing two emotion regulation strategies—cognitive reappraisal and expressive suppression. It will be used at the three assessment points to capture changes in emotion regulation during the study.

Brief Experiential Avoidance Questionnaire (BEAQ⁵⁶): The 15-item BEAQ is a modified, briefer version of the original 62-item Multidimensional Experiential Avoidance Questionnaire (MEAQ), self-report measure of six experiential avoidance domains: behavioral avoidance, distress aversion, procrastination, distraction/suppression, repression/denial, and distress endurance. It will be used at the three assessment time points to capture changes in experiential avoidance.

Overall Anxiety Severity and Impairment Scale (OASIS⁵⁷). This is a 5-item, self-report measure assessing the anxiety-related severity and impairment in the past week. It will be administered at each of the three assessment points to participants in both conditions. Participants in the UP + TAU condition will also complete it at the start of each UP session, per the treatment protocol³⁷.

Overall Depression Severity and Impairment Scale (ODSIS⁵⁸). This 5-item, self-report measure captures severity and impairment of depression in the past week. It will be administered at each of the three assessment points to participants in both conditions. Participants in the UP + TAU condition will also complete it at the start of each UP session, per the treatment protocol³⁷.

Self-Injurious Thoughts and Behaviors Interview-Clinician-Rated Version (SITBI-CR⁵⁰). This clinician-rated measure will be used to capture suicidal thoughts and behaviors and NSSI over lifetime, past year, past month, and past week at the screening/baseline visit.

Self-Injurious Thoughts and Behaviors Interview-Self-Report Version (SITBI-SR⁵⁰). This self-report measure will be used to capture suicidal thoughts and behaviors and NSSI in the past month at the mid-treatment and post-treatment assessments.

Timeline Follow Back (TLFB^{53,54}). The TLFB will be administered as an interview at all three time points in order to determine frequency and quantity of substance use, as well as percent days abstinent, since the last assessment (or at pre-treatment, over the past month). For the TLFB, participants mark the days on which they used a substance and indicate which substance(s) (and how much) they used.

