Patient Health Questionnaire (PHQ-9⁶³): A nine-item measure of depressive symptoms. It will be administered at each of the three assessment points to participants in both conditions.

Generalized Anxiety Disorder Assessment ($GAD-7^{64}$): A 7-item measure of generalized anxiety symptoms. It will be administered at each of the three assessment points to participants in both conditions.

Short Version of the UPPS-P Impulsive Behavioral Scale (SUPPS-P⁶⁵): A 20-item version of the original UPPS-P Impulsive Behavior Scale that assess five distinct facets of impulsivity: negative urgency, sensation seeking, lack of premeditation, lack of perseverance, and positive

urgency. It will be administered at each of the three assessment points to participants in both conditions.

*Emotion Reactivity Scale (ERS*⁶⁶): A 21-item self-report measure of emotion sensitivity, intensity, and persistence. It will be administered at each of the three assessment points to participants in both conditions.

Drug Use Motives Questionnaire (DUMQ^{67, 68}): An adapted version of the original Drug Use Motives Questionnaire; a 17-item measure to assess reasons or motives for using substances. It will be administered at the screening/baseline visit only.

Concomitant Treatment Log: A log that captures overall treatment plan, including therapy and medication, as well as the corresponding start and stop dates for each treatment. A study clinician will complete the log at the screening/baseline visit, and update the log at the mid- and post-treatment assessment visits.

Study clinicians and subjects will complete all measures on paper copies. Data collected will then be entered directly into REDCap by study staff.

Table 1 (below) outlines the schedule of assessments for the study.

Table 1. Schedule of Assessments

Assessment	Screen /Baseli ne	Week 1	Week 2	Week 3	Week 4 / Mid- treatment	Week 5	Week 6	Week 7	Week 8 / Post- treatment
Informed Consent	X								
Form									
Demographics/	X								
Contact Info Inclusion/	X								
Exclusion	X								
Adverse Events					X				X
Tracking Form					Λ				Λ
Concomitant	X				X				X
Treatment Log									
PHQ-9	X				X				X
GAD-7	X				X				X
SUPPS-P	X				X				X
ERS	X				X				X
DUMQ	X								
SITBI-CR	X								
SITBI-SR					X				X
BSI	X				X				X
CSS	X				X				X
Craving Scale	X				X				X
TLFB	X				X				X
ERQ	X				X				X
BEAQ	X				X				X
OASIS	X	X (UP +	X (UP +	X (UP +	X	X (UP +	X (UP +	X (UP +	X

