Week 7	Session 14	No	Emotion exposure (UP Module 7):
			-Present the rationale for conducting emotion exposure
	(Repeat		exercises (including the natural course of emotion)
	Session 12)		-Conduct emotion exposure exercise as a group (e.g.,
			imagining an emotional situation, listening to emotion-
			provoking music, or watching an emotional video
			while practicing new emotion management skills)
Week 8	Session 15	No	Relapse prevention (UP Module 8):
			-Review key treatment concepts and emotion
			management skills
			-Identify ongoing opportunities for skills practice
			-Identify long-term goals
Week 8	Session 16	No	Relapse prevention (UP Module 8):
			-Review key treatment concepts and emotion
			management skills
			-Identify ongoing opportunities for skills practice
			-Identify long-term goals
L	1		

VI. BIOSTATISTICAL ANALYSIS

Power: The proposed pilot study is the first, necessary step in obtaining preliminary data to justify future larger, randomized trials. Although we will test for statistical significance, the primary aim is to obtain usable feasibility and acceptability data, as well as to estimate the adjunctive intervention's effect size in order to conduct more adequately powered studies in the future. As such, a formal power analysis was not conducted *a priori*; however, the proposed N (50 subjects) is in line with other recent pilot RCTs examining the feasibility and preliminary efficacy of cognitive-behavioral group interventions for young adults⁶¹ and teens⁶² with SUD.

Preliminary analyses will describe the participants' demographic and clinical characteristics. Comparisons will be made using Mann-Whitney or chi-square tests to determine if the

randomization provided a balanced sample and if participants who dropped out differ from those who did not. All analyses will be conducted using the SPSS and/or Stata statistical packages.

Specific Aim 1: We will use descriptive statistics to report satisfaction ratings with the UP intervention (total CSQ-8 score; *Hypothesis 1a*) and number of UP sessions attended. We will use chi-square tests to evaluate differences in the proportion of participants in each condition who drop out of treatment at the ARMS program during the study period (*Hypothesis 1b*).

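### The post-treatment visit is dated from randomization in TAU but from the 16th session in UP + TAU, so UP blocks that must wait have a longer study period than controls

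*Protocol*

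**What the plan says.** Under V. Study Procedures, the TAU paragraph dates the post-treatment visit from randomization: "Eight to 10 weeks after randomization, they will repeat the same measures". The UP + TAU paragraph dates it from the intervention: "and the post-treatment assessment will occur within two weeks after each" participant's 16th UP session. The same section calls this visit the primary endpoint. The UP mid-treatment visit has a calendar alternative, "OR between 4-6 weeks after randomization", but the UP post-treatment visit has none.

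Under IV. Subject Enrollment, a block of five is randomized once its last member has completed baseline, wherever the UP group then stands in its cycle. Under Description of the UP Treatment, the course is 16 sessions over 8 weeks. New members may not enter in UP Weeks 6 to 8, and a block randomized then waits up to 4 weeks for the next UP Week 1.

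The contact rule in section V concerns participants in either condition who stop responding "at any point within the 10-week study, they will be considered dropped out from the study".

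Two hypotheses depend on the length of the study period. Hypothesis 2e predicts "lower quantity and frequency of substance use during the study period than those in the control condition". For Hypothesis 1b, section VI compares the proportions of participants "who drop out of treatment at the ARMS program during the study period". The Timeline Follow Back (TLFB) that supplies the use data covers the time "since the last assessment (or at pre-treatment, over the past month").

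**The concern.** In a randomized comparison, the period over which events and use are counted should not depend on the arm. Here it can. TAU participants always finish 8 to 10 weeks after randomization. A UP participant finishes when the course ends, and for some blocks the course starts late under the protocol's own entry rule. The delay can arise only in the UP arm, because only that arm waits for a group.

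For such a block there is more time in which to drop out of the outpatient program and more days on which to use substances. Both work against UP on Hypotheses 1b and 2e. The protocol also contradicts itself: a study described as lasting 10 weeks has not reached its primary endpoint at week 10 for these participants.

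**Working it through.** **Inputs.** TAU post visit: 8 to 10 weeks from randomization (section V). UP post visit: 0 to 2 weeks after session 16 (section V). Course: 16 sessions at two a week = 8 weeks (Description of the UP Treatment). Wait *w*: 0 to 4 weeks (same section). Stated study length: 10 weeks (section V).

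**Step 1: the plan's own figure.** UP post window = *w* + 8 to *w* + 8 + 2. With *w* = 0 this is weeks 8 to 10, which matches TAU and reproduces the 10-week study. The window may open a few days earlier, since session 16 falls within UP Week 8.

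**Step 2: delayed blocks.**

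| Wait (weeks) | UP post window | TAU window |
|---|---|---|
| 0 | 8–10 | 8–10 |
| 1 | 9–11 | 8–10 |
| 2 | 10–12 | 8–10 |
| 3 | 11–13 | 8–10 |
| 4 | 12–14 | 8–10 |

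At a 2-week wait the windows only touch. Beyond that, every permitted UP date lies after week 10. Back-to-back 8-week cycles imply at most 3 weeks (closed for Weeks 6, 7 and 8). Four weeks is the protocol's stated maximum.

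**Step 3: span covered by the TLFB.** The first TLFB interval after baseline starts at baseline, not at randomization. Let *b* be the weeks from baseline to randomization. The documents do not give it, so 0 to 4 is an assumed range. For a 4-week wait, the UP span relative to TAU is (12 + *b*)/(8 + *b*) at the early end of the windows and (14 + *b*)/(10 + *b*) at the late end:

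- *b* = 0: 12/8 = 1.50 and 14/10 = 1.40 (upper bound)
- *b* = 2: 14/10 = 1.40 and 16/12 = 1.33
- *b* = 4: 16/12 = 1.33 and 18/14 = 1.29

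At a constant daily rate, a total of use would grow by the same factor. Percent days abstinent and use per day would not.

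**Step 4: average over the arm.** Assume randomization is spread evenly over the cycle. With back-to-back cycles, 3/8 of UP participants wait, by 1.5 weeks on average: 3/8 × 1.5 = 0.56 week. If a gap week between cycles is what produces the 4-week cap, 4/9 wait, by 2 weeks on average: 4/9 × 2 = 0.89 week. At 2:1, about 33 of 50 participants are in UP, so about 12 to 15 would wait. Against a midpoint span of 9 + *b* weeks:

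- *b* = 0: 0.56/9 = 6.3% to 0.89/9 = 9.9% longer
- *b* = 4: 0.56/13 = 4.3% to 0.89/13 = 6.8% longer

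**Step 5: symptom scores.** OASIS, ODSIS and BSI ask about the past week and the SITBI-SR about the past month, so their recall windows do not change; only the date shifts. Assume usual care improves scores by 0.3 to 0.5 SD per 9 weeks. The arm-average shift is then 0.5625 × 0.3/9 = 0.02 SD to 0.889 × 0.5/9 = 0.05 SD. The standard error of a difference with about 33 versus 17 participants is √(1/33 + 1/17) = 0.30 SD, ignoring clustering. The shift is at most 0.049/0.299 = 0.17 of a standard error.

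**The case against.** The best defence is that dating the visit by the end of the course is deliberate. Aim 2 concerns acute efficacy from pre- to post-treatment. After a 4-week wait, a visit at weeks 8 to 10 would fall when only 2 × 4 = 8 to 2 × 6 = 12 of the 16 sessions had been offered. That stands, and it is why forcing the UP visit into the TAU window is not the remedy. It does not explain why dropout and use should be counted over unequal periods.

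It can also be said that normalizing use by days is ordinary content of a statistical analysis plan, and that no passage says totals will be analysed. That is fair, and the ratios in Step 3 apply only if totals are used. Even so, the protocol itself states the visit dates, the wait and the 10-week length, and these conflict. An analysis plan cannot settle when visits occur.

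A reader might infer more than the documents support:

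- *That the whole UP arm is assessed late.* Only blocks randomized while entry is closed are, and 12 to 14 weeks is the stated maximum.
- *That use is inflated by half.* That is the upper bound, with no time between baseline and randomization and with totals analysed.
- *That Table 1 contradicts the text because it places the visit under* "Week 8 / Post- treatment". Its intermediate columns hold only measures given at UP sessions, so the columns can be read as treatment weeks, and a delayed block then still fits.
- *That people who miss sessions have no visit date.* The protocol does not say whether the 16th session means held or attended. Sessions are offered on a numbered schedule with no limit on absences, so the scheduled reading is the natural one. This calls for clarification and is not an error.
- *That the wait has no limit because a group may be slow to form.* No maximum is stated for that wait, but the text does not say that it follows randomization, so it is not counted here.

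**Conclusion.** The inconsistency is real and minor. The protocol gives the primary-endpoint visit different anchors in the two arms, and its own entry rule can place that visit at weeks 11 to 13 (3-week wait) or up to weeks 12 to 14 (stated maximum) in UP, against 8 to 10 in TAU and a stated 10-week study. For those blocks the study period for Hypotheses 1b and 2e is longer in the UP arm only, to UP's disadvantage.

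The window arithmetic rests only on stated figures. The TLFB ratios rest on the assumed interval from baseline to randomization and on totals being analysed. The share of participants who wait, and the shift in symptom scores, rest on even randomization over the cycle and an assumed usual-care trend. On those assumptions the symptom effect is negligible beside the precision of a 50-person pilot. The case for acting is that one arm-dependent period can be removed at almost no cost.

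**What to change.** Reconcile the TAU, UP + TAU and contact-rule paragraphs of section V with the waiting rule in Description of the UP Treatment.

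1. Define the study period as the same fixed period from randomization in both arms. Count Hypothesis 1b dropout over it (for example, the stated 10 weeks), and analyse TLFB use over that period or as a rate per day.
2. State that the UP post-treatment visit follows the block's scheduled course, and set its calendar date at randomization for every UP participant, regardless of attendance. Adjust the 10-week wording so that it does not exclude that visit.

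Both are changes of wording. The cost to state openly is that, for delayed blocks, the fixed period includes the wait before UP begins, so it captures less of the course.

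The sponsor may also weigh randomizing a completed block only when the UP group is open to entry. One 8-to-10-week window would then serve both arms with all 16 sessions offered. In return, some baselines would be up to 3 to 4 weeks older and some people might be lost before randomization, with neither effect depending on the arm. This is an option and not a required change.

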measures of anxiety or depression used for clinical purposes at ARMS, and/or report of suicidal thoughts or NSSI in the past week) will be enrolled in the study. An ARMS clinician will determine possible subject eligibility based on information obtained during the routine clinical evaluation for ARMS treatment. Those who are deemed potentially eligible and express interest in the study will then undergo a brief in-person screening visit with a study clinician. The screening visit, which will take about 60 minutes, will consist of a meeting with a study clinician to provide informed consent and confirm study eligibility (via review of information obtained during routine ARMS clinical care and completion of the SITBI-CR). For participants who report suicidal thoughts in the past week or having made a suicide plan or suicide attempt in the past year on the SITBI-CR, a clinical risk assessment (including severity of ideation and presence of plan, intent, and access to means) will be conducted during the visit in order to ensure participant safety and eligibility for the study (i.e., no imminent suicide risk). The study clinician conducting the screening visit will consult the ARMS Clinical Director (or, if [name] is unavailable, another licensed clinician on-site) immediately regarding risk in any questionable cases to determine the appropriate action, per usual ARMS clinical procedures. Eligible participants will then complete the Timeline Follow Back (TLFB^{53,54}) as an interview, in which participants recall the quantity and frequency of substance use during a specified time window (e.g., past month) using a calendar, and several self-report questionnaires, including the BSI, CCS, and Craving Scale (see Table 1). The study clinician will also fill out a concomitant treatment log to identify the participant's overall treatment plan, including medication and therapy. Data obtained at this screening visit will be considered the "pre-treatment" assessment. After eligibility criteria are determined and participants have completed the screening/baseline assessment, participants will be randomly assigned to UP+TAU or TAU only conditions using a permuted block randomization procedure. The permuted block randomization schedules will be generated by an independent biostatistician from the MGH Biostatistics Center prior to enrolling the first subject into the study. Groups, or "blocks," of 5 individuals will be randomized at a time to one of the two treatment conditions (UP+TAU or TAU alone) using a 2:1 randomization scheme, defined as 2 blocks randomized to UP + TAU for every 1 block randomized to TAU alone. Randomizations will be conducted using a web-based randomization program developed by the MGH Biostatistics Center. The randomization code will be generated within the webbased program by study staff only when the randomization occurs, i.e. once the last participant of each group has completed baseline. Participants will then be contacted by study staff via their preferred method of communication to notify them of their study condition.

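### The follow-up risk-assessment trigger omits past-month suicidal behavior on the SITBI-SR and past-week ideation or plans on the BSI, which leaves a gap mainly for questionnaires completed by link

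*Protocol*

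**What the plan says.** **Screening (Section IV).** A risk assessment is done for past-week suicidal thoughts and, as a separate criterion, for "having made a suicide plan or suicide attempt in the past year on the SITBI-CR, a clinical risk assessment".

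**Mid- and post-treatment, in person (Section V, TAU condition).** The assessment is done "should a participant report suicidal thoughts in the past week on the SITBI-SR or clinically significant increases in NSSI". The UP + TAU paragraph adopts the same procedure.

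**Questionnaires completed by link (Section V).** Staff look through the submission within 24 business hours for suicidal thoughts. The call rule reads "Should a participant report suicidal thoughts in the past week on the SITBI-SR, a clinical risk assessment" and is carried out by phone. A clinically significant rise in NSSI also leads to a call. Plan, intent and means appear only as topics of the assessment once it has been triggered.

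**What the forms collect (Section V, measures list; Table 1).** The SITBI-SR covers suicidal thoughts, suicidal behaviors and NSSI over the past month at mid- and post-treatment. The BSI covers attitudes, behaviors and plans over the past week at all three assessments.

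**Clinician contact.** Follow-up assessments include a part done with a clinician ("plus TLFB and concomitant treatment log with a study clinician"), which may be done by phone. Section IX has a study clinician assess suicidality, including plan, intent and means, and monitor adverse events at each assessment visit.

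**The concern.** The protocol collects two kinds of report at follow-up that its own rule does not require anyone to act on: suicidal behavior in the past month on the SITBI-SR without past-week thoughts, and past-week ideation or plans given on the BSI alone. At screening, a plan or attempt is enough by itself. At follow-up, a more recent attempt is not, and no reason is given.

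Participants can qualify for the trial through past-week suicidal thoughts or NSSI (inclusion criterion 7), so such reports are foreseeable. When the form is completed by link, no clinician need be present. What is at stake is whether a reported attempt must lead to a clinician contact. The rule is the same in both arms, so bias between arms is not in question.

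**Working it through.** No arithmetic applies. The check sets the trigger rules beside what the forms collect, and then asks whether another rule closes the gap.

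**Step 1. Which reports trigger an assessment?**

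| Report | Screening (Section IV) | Mid/post, in person or by link (Section V) |
|---|---|---|
| Past-week suicidal thoughts | Yes, on SITBI-CR | Yes, on SITBI-SR |
| Attempt within the past month, no past-week thoughts | Yes, on SITBI-CR (falls within the past year) | Not named |
| Plan within the past month, no past-week thoughts | Yes, on SITBI-CR (falls within the past year) | Not named; the protocol does not say whether the SITBI-SR asks about plans |
| Past-week ideation or plans on the BSI only | BSI not named | Not named |
| Clinically significant NSSI increase | Not named | Yes |

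The comparison with screening therefore supports the point for plans and attempts. It does not bear on the BSI, which is not a trigger at either stage. The BSI part rests on the form covering past-week plans and behaviors while the call rule names only the SITBI-SR.

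**Step 2. Does another rule cover these reports in person?** Largely, yes. The Section IX assessment needs no questionnaire answer to set it off, and it asks about plan, intent and means. Adverse-event monitoring is scheduled at the same visits.

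**Step 3. Does another rule cover them when the form comes by link?**
- The Section IX assessment attaches to assessment visits. The text does not say that it applies when the visit is done by phone.
- The phone option for clinician-rated measures requires a risk assessment if a risk issue arises. It does not direct the clinician to the link answers.
- The round-the-clock pager and emergency psychiatry access in Section IX depend on the participant seeking help.
- The 24-business-hour review looks for suicidal thoughts. It could bring BSI ideation to staff attention, but the stated action depends on the SITBI-SR.

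None of these requires the clinician contact to come after the link submission or to respond to it. If the contact comes later, the Section IX assessment would probably pick up the report. If it comes first, the Section V call rule is the only stated response to the link answers, and that rule does not name these reports. At post-treatment no later study assessment follows: "After completing the post-treatment assessment, their participation in the study will be complete".

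**Step 4. Is baseline affected?** Hardly. A clinician completes the SITBI-CR at screening, with the wider trigger.

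**The case against.** The strongest reply is that Section V sets a minimum on top of a broader safety plan. Section IX already has a clinician ask about plan, intent and means at each assessment visit. Adverse events are monitored, every participant has a clinician on call, and consent to exchange data with the treating program is required for entry. Nothing stops a clinician from calling after reading a reported attempt. This stands for in-person visits and is why the point is modest. It does not fully answer the link route, for which the authors wrote a separate review-and-call rule that is narrower than what the forms collect.

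Three further replies also have force:
- The screening rule partly serves eligibility, since imminent suicide risk is an exclusion, so a different follow-up threshold is not in itself a contradiction. Even so, a past-month attempt bears on safety at any stage.
- The protocol says that the SITBI-SR covers suicidal behaviors but does not document a plan item.
- BSI-only reports should be uncommon, because the person would have to deny past-week thoughts on one form and endorse them on the other.

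A reader might infer a possible delay of up to 14 days from the scheduling windows: "Four to 6 weeks after randomization, TAU participants will complete a mid-treatment assessment"; "Eight to 10 weeks after randomization, they will repeat the same measures"; and, for UP + TAU, "the post-treatment assessment will occur within two weeks after each" participant's last session. The documents do not support that figure. These windows say when an assessment is held. The protocol treats the clinician-rated measures as one portion of the visit and nowhere provides for splitting it across a window.

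**Conclusion.** The point holds in limited form. The follow-up trigger, in person and by link, is narrower than what the SITBI-SR and BSI collect, and narrower than the screening rule for plans and attempts. Section IX and the other safeguards largely cover in-person visits. What remains is mainly the link route, where no text makes a clinician contact follow or respond to the submitted answers.

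The size cannot be given. The protocol states neither the share of remote completions nor a rate of plans or attempts, and no delay follows from its text. A reader might also infer that suicidality goes unassessed at follow-up, or that the narrow trigger is peculiar to the link. Section IX rules out the first and the in-person rule rules out the second.

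The conclusion assumes that the SITBI-SR can record suicidal behavior without past-week thoughts, which its stated content and past-month period suggest. It does not depend on a plan item. Priority is low to moderate: a participant-safety improvement that leaves endpoints and the arm comparison untouched.

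**What to change.** - **Section V, completion by link.** Widen the 24-business-hour review and the phone risk-assessment trigger to include (a) any suicide attempt or other suicidal behavior in the past month on the SITBI-SR, including a plan if the form asks about one, and (b) past-week ideation or plans on the BSI. Keep the existing triggers for past-week thoughts and NSSI.
- **Section V, TAU condition.** Use the same wording for in-person assessments. It then carries over to UP + TAU.
- **Section IX, Safety Monitoring.** State that the clinician suicidality assessment also applies when a visit is done by phone.

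This is a wording amendment. It needs no new measure or visit and uses answers that are already collected and looked through within 24 business hours. The cost is a small number of extra risk-assessment calls, which the protocol gives no basis for counting.
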